7.4 Subjects

7.4.1 Inclusion and Non-Inclusion Criteria

The study investigators will screen patients and evaluate their eligibility for this study. Patients will not be enrolled in the study unless they meet all of the inclusion criteria and none of the non-inclusion criteria.

7.4.1.1 Inclusion Criteria

1. Subject is undergoing an open cardiac procedure by median sternotomy
2. Subject is at risk of prolonged mechanical ventilation according to one or more of the following criteria:
 - Prior open cardiac surgery
 - Left Ventricular Ejection Fraction (LVEF) ≤ 30%
 - History of TIA or CVA
 - Pre-operative or anticipated intraoperative intra-aortic balloon pump
 - History of COPD
3. Subject is at least 22 years of age
4. Informed consent has been obtained from the patient

7.4.1.2 Non-Inclusion Criteria

1. Subject is on invasive mechanical ventilation prior to procedure
2. Subject has known or pre-existing phrenic nerve paralysis
3. Subject is having a left ventricular assist device implanted
4. Subject has progressive, non-reversible neuromuscular disease affecting the diaphragm
5. Subject is pregnant or lactating
6. Subject is actively participating in another clinical study which could affect outcomes in this study

7.4.2 Point of Enrollment

30 subjects will receive TransLoc electrodes. Subjects from whom informed consent is obtained are enrolled in the study. Subjects will be randomized to:

Group 1: Tx (Treatment with TransAeris stimulation upon completion of procedure), or;

Group 2: SOC (Control with cross-over to Treatment if still on MV at 120 hours post-op).

7.4.2.1 Randomization

Subject randomization list will be created prior to the start of the study using a block randomization technique. Subject randomization letters will be provided in sealed envelopes in each subject binder. All subject binders will be maintained in the site's clinical research department. Each envelop will be unsealed prior to surgery, and after the subject has signed the consent form.

7.4.3 Subject Withdrawal or Discontinuation

All subjects enrolled in the clinical study shall be accounted for and documented. If a subject withdraws consent before implantation of the TransLoc electrodes, all study-related activities will end. If the subject is implanted with the TransLoc electrodes and withdraws consent, all study-related activities will end and the electrodes will be removed. If the investigator withdraws the subject from the clinical investigation, all study-related activities will end and the reason(s) for withdrawal shall be reported.

7.4.4 Procedures for Replacement Subjects

Subjects that do not have the TransLoc electrodes inserted during their primary surgery will be withdrawn from the study and a replacement will be assigned. The reason for not placing the electrodes will be documented on the Study Exit form for non-implanted patients. Additionally, a chart review will be performed for the non-implanted patients to record their time on mechanical ventilation time, length of ICU and hospital stay and any complications that they experienced during their post-operative stay. Since these patients are consented, this information will be evaluated to determine any relation to their reason for not being implanted to their outcomes and the inclusion criteria.

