1. PROTOCOL SYNOPSIS

Title	Randomized Study of TransAeris® system for Enhanced Recovery After Surgery (ERAS) in cardiac surgery patients in France at risk of prolonged mechanical ventilation
Protocol Number	20-1000-108
Device Tested	TransAeris® System
Purpose	This study will be conducted as a randomized trial of the TransAeris system for the prevention and treatment of ventilator-induced diaphragm dysfunction (VIDD) in patients identified prior to surgery to be at greater risk of prolonged mechanical ventilation (PMV).
Study Objectives	
The specific objectives of this study are:
 
Primary objective:
 
• Evaluate the credibility of expected treatment benefits 
Secondary objectives:
 
• Identify safety concerns• Identify barriers to enrollment• Evaluate the randomized protocol in single site setting, prior to multi-center expansion• Assess the capability of collecting the specified evaluation criteria• Assess the capability to quantify diaphragm electrical activity through diaphragm EMG monitoring
Study Design	This study is an open label, randomized, cross-over study in adult open cardiac surgery patients. All subjects will receive TransLoc electrodes at the time of open sternotomy cardiac procedure. Half of subjects will have TransAeris turned on upon entry to ICU, the other half will receive standard of care with TransAeris turned on if still intubated on mechanical ventilation after 120 hours.

Outcome Measures	
Primary Safety: Incidence of Serious Device Related Adverse Events
 
Primary Efficacy: Mechanical ventilation time and proportion of patients weaned at 48- and 120-hours post-op
 
Ancillary Outcomes:
 
Safety:
 
 Interference with ICU care Device related adverse events 30-day mortality 
Efficacy:
 
 Time on mechanical ventilation 
 – measured in hours from entry to ICU and reversal of paralytics EMG analysis of cross-over patients Ventilator Free Days Length of stay, ICU & Hospital
Enrollment	30 subjects will be randomized prior to surgical placement of TransLoc electrodes
Participating Site	1 French site will participate in this study

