7. DESIGN OF THE CLINICAL INVESTIGATION

7.1 Type of Clinical Investigation

This study is a monocentric and open label randomized study in adult open cardiac surgery patients. Eligible patients from whom informed consent is obtained are enrolled in the study. All subjects will be implanted with the TransLoc electrodes during their primary surgery. Patients are randomized to treatment or control groups prior to surgical placement of the TransLoc electrodes.

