7.5.1.3 Electrode Placement and Device Use

All subjects will be randomized to treatment or control groups prior to implantation of the TransLoc electrodes. Subjects not implanted will be withdrawn from the study. The procedure information is recorded on the case report form, page 4. Specific information concerning the cardiac procedure that the patient is undergoing is recorded on the form as well as procedure time, pump time and any concomitant interventions that the patient undergoes at the time of the cardiac surgery. The device tracking information for the electrodes are recorded in the procedure information as well as an indication of successful electrode placement, or occurrence of an adverse event, competing event or device deficiency.

Patients are randomized to the Treatment or Standard of Care groups as per section 7.4.2.1. The group assignment is recorded on the Post-Op case report form, page 5. This case report form is completed for each patient for each day in protocol, beginning with the day of surgery as day 0. The reversal or time when paralytics are worn off is recorded as well as the current ventilatory support in terms of intubation, extubation, and any type of post-extubation ventilatory support that may be required.

Once the paralytics have been reversed from the surgery, an initial diaphragm EMG is recorded on case report form, page 6. If bilateral EMG is not observed, then a competing event is recorded as described below in section 7.5.1.4.

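### Randomised patients who are not implanted are withdrawn and replaced after the envelope has been opened, so removal with the arm known is possible; the number randomised and the place of these patients in the arm comparison need settling

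*Combined protocol and SAP*

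**What the plan says.** Section 7.1 gives the design: "This study is a monocentric and open label randomized study in adult open cardiac surgery patients". Section 7.4.2.1 sets the time at which the arm is revealed: "Each envelop will be unsealed prior to surgery, and after the subject has signed the consent form". Section 7.5.1.3 puts randomisation before implantation in both arms and adds: "Subjects not implanted will be withdrawn from the study". Section 7.4.4 says that such patients "will be withdrawn from the study and a replacement will be assigned". Table 2a lists randomisation in the column for the time of surgery. On either reading the arm can be known before the electrodes go in.

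Two counts are given. The synopsis says "30 subjects will be randomized prior to surgical placement of TransLoc electrodes"; section 7.4.2 says "30 subjects will receive TransLoc electrodes". Section 8.5 speaks of implanting up to 30 and expects that some consented patients will not be implanted.

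On what happens to the non-implanted, 7.4.4 says: "The reason for not placing the electrodes will be documented on the Study Exit form for non-implanted patients". It also orders a chart review of ventilation time, ICU and hospital stay, and complications, and states its use: "this information will be evaluated to determine any relation to their reason for not being implanted to their outcomes and the inclusion criteria". Section 7.4.2 treats consented patients as enrolled, 8.3 bases the primary analysis on everyone enrolled, and 8.7 keeps whatever data exist on drop-outs.

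**The concern.** Withdrawing and replacing patients after randomisation is harmless only if the decision not to implant has nothing to do with the arm and prognosis taken together. The text gives no criteria for not implanting and describes no step that keeps the surgeon unaware of the arm. It also does not say which arm a replacement joins (the flowchart in Figure 1 is not available to me). Section 4.2 describes electrode placement as a short step at the end of the operation, so the decision can follow the intraoperative course. The electrodes' expected use also differs by arm: a control patient is stimulated only if still ventilated at 120 hours, which section 4.2 expects for 2 to 3 of 15.

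The study tests no hypothesis, but section 8.1 wants its data to inform the design and statistical parameters of the pivotal trial. One of its objectives is to try out the randomised protocol before multi-centre expansion. An interval shows sampling error; it does not show selective removal. Separately, two analysts could reasonably disagree on whether a randomised, non-implanted patient belongs in the arm comparison.

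**Working it through.** **The plan's own figures.** The 30 for this trial comes with no calculation to reproduce. The inputs for size come from section 4.2:
- Predictive value of the risk criteria for prolonged ventilation: 13/23 = 56.5%.
- Prolonged-ventilation patients still ventilated at 48 h: control 73,391/111,307 = 65.9%; treatment 65.9% − 20 points = 45.9%.
- As a check on the chain, 15 × 0.565 × 0.348 = 2.9 controls ventilated at 5 days, in line with the plan's 2 to 3.

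**Expected proportion ventilated at 48 h among all patients.**
- Control: 0.565 × 0.659 = 0.372.
- Treatment: 0.565 × 0.459 = 0.259.
- Difference: 11.3 points. This is implied by the plan's inputs; it is not a stated target.

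**Effect of one swap.** Suppose one patient whose chance of being ventilated at 48 h is q is dropped from an arm of 15 with average p, and is replaced in the same arm by an average patient. The expected shift is (q − p)/15.

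| Assumption | Control | Treatment | Share of 11.3 points |
|---|---|---|---|
| Non-implantation unrelated to prognosis (q = p) | 0 | 0 | 0 |
| Prolonged-ventilation patient identified with certainty | (0.659 − 0.372)/15 = 1.9 points | (0.459 − 0.259)/15 = 1.3 points | 12% to 17% |
| Status at 48 h foreseen with certainty (q = 1) | (1 − 0.372)/15 = 4.2 points | (1 − 0.259)/15 = 4.9 points | 37% to 44% |

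The second and third rows are both upper limits for the knowledge they assume. All patients already meet at least one risk criterion, and the predictive value of the criteria is only 56.5%.

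**Sampling error.** SE = √(0.372 × 0.628/15 + 0.259 × 0.741/15) = 0.168, and 1.96 × 0.168 gives ±33 points.

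**How many might be replaced.** The plan gives no rate. In the pilot, 44 consented (4.2) and 32 were implanted (4.1), so 12/44 = 27% were not implanted, exact 95% interval about 15% to 43%. If that rate applied after randomisation, 30 implants would need 30/(32/44) = 41.25, so 42 randomised; the interval gives 36 to 53. At an assumed 5%, 30/0.95 = 31.6, so 32. The pilot rate is for consented patients, came from a study that used nine risk factors rather than five, and has an uncertain denominator (the counts in 4.2 are 14 + 29 = 43).

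**Analysis set, side by side.** Sections 7.4.2, 8.3 and 8.7 together lean towards including the non-implanted. Section 7.4.4 withdraws and replaces them, and puts their chart review to a use other than the arm comparison. Section 8.5 says only that they are to be documented and accounted for.

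**Data, if they count.** Section 8.4.2 defines a successful wean by absence of reintubation within 48 hours of extubation, and 8.4.3 includes 30-day mortality. The chart review does not expressly list extubation or reintubation times or 30-day vital status. The questionnaire that records survival (7.5.1.6) is for implanted patients. Table 2a lists ventilation start and stop times for all patients initially, but does not make clear whether that covers those already withdrawn.

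**The case against.** The strongest reply is that selection here is conjecture. Both arms are to be implanted, and controls need the electrodes for EMG and for a possible cross-over at 120 hours. Reasons for not implanting are recorded, and the group is entered only on the post-operative form. A reader might infer from the sequence that the plan builds in arm-driven exclusion. The documents do not support that; they leave the route open and no more.

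A second reply is that the analysis set is already settled by 7.4.2, 8.3 and 8.7. A reader might go the other way and call 7.4.4 a contradiction of 8.3. Neither holds. Being withdrawn does not by itself mean being left out of the analysis, and 8.7 keeps data on drop-outs, but nothing commits the plan to counting these patients by arm.

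Third, the data gap should not be overstated: reintubation or in-hospital death could fall under complications in the chart review, and Table 2a may supply ventilation times.

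Fourth, the study is descriptive, section 4.2 expects it to be statistically inconclusive, and one swap is small beside ±33 points. That lowers the stakes. It does not remove the reason to close a route to bias that costs little to close.

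**Conclusion.** The point stands as an avoidable design weakness that should be fixed, with two items to reconcile.

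Removal after the arm can be known is possible under the rules as written. Its effect is zero if non-implantation is unrelated to prognosis. Otherwise each selective swap moves an arm by up to 1.3 to 1.9 points or, at the extreme, 4.2 to 4.9 points, in a direction that depends on the arm and on who is dropped. These figures assume 15 per arm, the rates in section 4.2, and a replacement who joins the same arm. Sampling error is much larger, so this bias would not dominate the result.

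The counts in the synopsis and 7.4.2 cannot both hold once anyone is replaced. A reader might add 8.5 to that conflict, but its figure is a maximum, and 30 randomised with fewer implanted satisfies it. A reader might also take the pilot's 27% as a ceiling or as the expected loss after randomisation. It is neither: it is a small-sample rate among consented patients, usable only as an illustration.

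**What to change.** 1. In the synopsis, 7.1, 7.4.2.1, 7.5.1.3 and Table 2a, have the envelope opened only once electrode placement is confirmed at the end of surgery. The arms differ only after surgery, so this fits the existing treatment start in 7.4.2. Non-implanted patients then become failures before randomisation, covered by the existing chart review. No randomised patient is replaced for non-implantation, and 30 randomised equals 30 implanted.
2. In 8.3, define the primary set as all randomised patients in their assigned arm. This is needed alongside the first change because 7.4.2 counts everyone who consents as enrolled.

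The cost is protocol wording and a later envelope step, with no extra patients or procedures. The envelopes are kept in the clinical research department, so they must be reachable at the end of surgery, including out of hours. Later opening does not by itself stop allocations being guessed in a blocked, open-label, single-site trial.

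If randomisation must stay before surgery:
- State in 8.3 and 8.7 that non-implanted patients are analysed in their assigned arm using the chart review.
- Add extubation and reintubation times and 30-day vital status to that review.
- State which arm a replacement joins.
- Give separate numbers for randomised and implanted.
- Report non-implantation with reasons by arm.

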7.4.5 Enrollment Period and Duration of the Clinical Investigation

It is estimated that enrollment will last approximately four months. The estimated duration of the study from first enrollment to last follow-up is six months. Total study duration per subject is estimated less than 60 days from screening to last follow-up day.

7.5 Procedures

7.5.1 Description of Investigational Procedures

Table 2 lists the data to be collected at each study interval. Study activities are recorded on the case report forms by the clinical coordinator or other clinician designated by the principal investigator. The clinician completing the form signs in the entry designated for completion and the principal investigator reviews all forms and signs in the designated location to indicate review and confirmation of the data entered.

Table 2a: Schedule of Study Activities and Data Collection – Initial All Patients

Activity/Procedure/ Assessment	Screening and Enrollment	At Time of Cardiac Surgery	ICU
Informed Consent	X		
Inclusion/non-inclusion criteria	X		
Demographics, medical history	X		
TransLoc electrode insertion		X	
Concomitant Interventions		X	
Serious adverse events		X	
Adverse device effects		X	

Activity/Procedure/ Assessment	Screening and Enrollment	At Time of Cardiac Surgery	ICU
Device deficiencies		X	
Randomization		X	
Concomitant Interventions			X
Start / Stop date and time of MV use			X
EMG Baseline recording			X

Table 2b: Schedule of Study Activities and Data Collection – Treatment Patients

Activity/Procedure/ Assessment	ICU
Start / Stop date of TransAeris stimulation	X
Competing events	X
Serious adverse events	X
Adverse device effects	X
Device deficiencies	X

Table 2c: Schedule of Study Activities and Data Collection – Control Patients

Activity/Procedure/ Assessment	ICU First 120hrs	ICU At 120hrs	ICU After 120hrs
EMG VIDD Progression recording		X	
TransAeris Start & Settings		X	
TransAeris Start/Stop & Settings			X
Competing events	X	X	X
Serious adverse events	X	X	X
Adverse device effects	X	X	X
Device deficiencies	X	X	X

Table 2d: Schedule of Study Activities and Data Collection – Conclusion All Patients

Activity/Procedure/ Assessment	Discharge	30 Days Post Electrode Removal
Serious adverse events	X	X
Adverse device effects	X	
Device deficiencies	X	
EMG Wean/Discharge recording	X	
TransLoc electrode removal	X	
Follow-up questionnaire		X

7.5.1.1 Screening and Enrollment

Subjects who have been identified prior to surgery to be at risk of prolonged mechanical ventilation after surgery are eligible for this study. Potential subjects will be screened by the investigator for eligibility in the study with respect to the inclusion and non-inclusion criteria (sections 7.4.1.1 – 7.4.1.3). Potential subjects who meet the inclusion and non-inclusion criteria and give informed consent will have demographic, screening, and medical history information including:

- Height
- Weight
- Gender
- Month and Year of birth
- Pregnancy test for women of child-bearing potential
- Admitting diagnosis
- Surgical procedure
- Medical history

Enrollment, demographic information and medical history on documented on case report forms page 1, 2 and 3, respectively.

7.5.1.2 Prolonged Mechanical Ventilation Risk Identification

Prolonged Mechanical Ventilation (PMV) for the purpose of this study is defined as ≥ 24 hours on mechanical ventilation post-surgery. If the patient meets the other inclusion / non-inclusion criteria and has any of the following risk factors for PMV then they will be included if they give informed consent. At least one of the risk factors below must be answered YES on the case report form.

1. Pre-operative or anticipated intraoperative IABP
2. Any prior open cardiac surgery
3. LVEF $\leq 30\%$
4. History of TIA or CVA
5. History of COPD

The specific risk factors met are to be documented on the enrollment case report form, page 1.

For those undergoing procedures where the STS risk calculator (riskcalc.sts.org) can provide a score, those scores will be calculated and the risk score of PMV for the specific patient will be entered on the case report form, page 2. The risk score and variables will be documented in the case history.

7.5.1.3 Electrode Placement and Device Use

All subjects will be randomized to treatment or control groups prior to implantation of the TransLoc electrodes. Subjects not implanted will be withdrawn from the study. The procedure information is recorded on the case report form, page 4. Specific information concerning the cardiac procedure that the patient is undergoing is recorded on the form as well as procedure time, pump time and any concomitant interventions that the patient undergoes at the time of the cardiac surgery. The device tracking information for the electrodes are recorded in the procedure information as well as an indication of successful electrode placement, or occurrence of an adverse event, competing event or device deficiency.

Patients are randomized to the Treatment or Standard of Care groups as per section 7.4.2.1. The group assignment is recorded on the Post-Op case report form, page 5. This case report form is completed for each patient for each day in protocol, beginning with the day of surgery as day 0. The reversal or time when paralytics are worn off is recorded as well as the current ventilatory support in terms of intubation, extubation, and any type of post-extubation ventilatory support that may be required.

Once the paralytics have been reversed from the surgery, an initial diaphragm EMG is recorded on case report form, page 6. If bilateral EMG is not observed, then a competing event is recorded as described below in section 7.5.1.4.

7.5.1.3.1 Treatment (Tx) Group

TransAeris use begins, in the Tx group as soon as practical. TransAeris stimulation will not begin unless the patient is connected to cardiac monitoring. The cardiac rhythm will be observed for any potential cardiac capture when stimulation is initiated, or any changes are made. The observation of cardiac rhythm interaction is recorded with the stimulator settings on the daily post-op case report form, page 5. TransAeris stimulator settings (stimulus intensity, stimulus frequency, and burst on/off) will be programmed to optimize diaphragm recruitment without compromising patient comfort. Refer to section 3.6.4.2 Device Programming. If stimulation settings cannot be adjusted or the stimulation cannot be applied without eliciting patient discomfort or pain due to the stimulation, then an adverse event indicated on the daily post-op case report form and an adverse event case report form, page 11, should be completed. Stimulation pain should be assessed daily using verbal and/or non-verbal cues from the patient using the visual analog scale shown below. In the event of pain that cannot be eliminated by reducing stimulation intensity then it should be recorded as such on the adverse event case report form.

TransAeris stimulation will continue as needed until the patient is successfully weaned. Stimulation may continue beyond successful weaning at the clinician's discretion to provide any additional support to avoid reintubation, but no longer than 30-days post-op.

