3.6.4.2 Device Programming

The TransAeris stimulator is programmed for the patient with intensity and frequency set up to elicit diaphragm recruitment without pain or discomfort from the stimulation. The clinician may program the intensity of each channel to optimize diaphragm recruitment. Frequency creates a tetanic or fused diaphragm contraction. Frequency affects all four channels and is set by the clinician to create a fused contraction. The pulse bursting is used to increase patient comfort with the stimulation. The trade-off of burst modulation settings is a reduction in diaphragm recruitment.

The stimulator has four independent channels of stimulation. The stimulation is a charge balanced, capacitively coupled current-regulated waveform. The maximum charge per cathodic phase is 5 μ C. The charge is calculated as the Cathodic Current (Ic) times the Cathodic Pulse Duration (PW). Stimulus waveforms can be selected as single cathodic pulse followed by the anodic recharge phase or as a burst of four cathodic pulses followed by the anodic recharge. The latter, burst mode stimulation, delivers the cathodic charge at a lower amplitude (1/4 of the single pulse value) and distributes four cathodic pulse at 1ms intervals. The burst mode stimulation may be selected to overcome a patient's reported stimulation discomfort.

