5.2 Anticipated Adverse Device Effects

The theoretical risks related to the study device are listed below, with the observed occurrence in the pilot study:

- Stimulus interferes with heart rhythm; 0 occurrences out of 10 patients
- Stimulus interaction with implanted cardiac defibrillator or cardiac pacemaker; 0 occurrences out of 10 patients
- Pain due to stimulation; 0 occurrences out of 10 patients
- Percutaneous electrode exit site infection requiring antibiotics; 0 occurrences out of 10 patients

The theoretical risks related to the procedure to insert or remove the TransLoc electrodes are listed below, with the observed occurrence in the pilot study:

- Bleeding during surgery due to insertion of the electrode; 0 occurrences out of 32 patients
- Tissue or organ damage during surgery due to insertion of the electrodes; 0 occurrences out of 32 patients
- Breakage of electrode lead; 0 occurrences out of 128 electrodes
- Accidental dislodgement of electrode from diaphragm; 1 occurrence out of 128 electrodes
- Unintentional device fragment retained after removal of electrode; 0 occurrences out of 108 removals
- Bleeding after removal of the electrodes; 0 occurrences out of 32 patients
- Exit site pain after removal of the electrodes; 0 occurrences out of 32 patients

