15. ADVERSE EVENTS, ADVERSE DEVICE EFFECTS AND DEVICE DEFICIENCIES

15.1 Definitions as per ISO 14155:2020 & MDR 2017/745

Adverse Event (AE): Any untoward medical occurrence, unintended disease or injury or any untoward clinical signs, including an abnormal laboratory findings, in subjects, users or other persons, in the context of a clinical investigation, whether or not related to the investigational medical device.

Note 1: This definition includes events related to the investigational medical device or the comparator.

Note 2: This definition includes events related to the procedures involved.

Note 3: For users or other persons, this definition is restricted to events related to the use of investigational medical devices or comparators.

Adverse Device Effect (ADE): Adverse event related to the use of an investigational medical device.

Note 1: This definition includes adverse events resulting from insufficient or inadequate instructions for use, deployment, implantation, installation, or operation, or any malfunction of the investigational medical device.

Note 2: This definition includes any event resulting from use error or from intentional misuse of the investigational medical device.

Note 3: This includes 'comparator' if the comparator is a medical device.

Serious Adverse Event (SAE): Any adverse event that led to any of the following:

a) Death,

b) serious deterioration in the health of the subject, that resulted in any of the following:

1) a life-threatening illness or injury,

2) a permanent impairment of a body structure or a body function,

3) hospitalization or prolongation of patient hospitalisation

4) medical or surgical intervention to prevent life-threatening illness or injury, or permanent impairment to a body structure or a body function,

5) chronic disease,

c) foetal distress, foetal death or a congenital physical or mental impairment or birth defect

Note 1: Planned hospitalization for a pre-existing condition, or a procedure required by the CIP, without serious deterioration in health, is not considered a serious adverse event.

Events that do not meet these criteria are considered non-serious.

Serious Adverse Device Effect (SADE): Adverse device effect that has resulted in any of the consequences characteristic of a serious adverse event.

Unanticipated Serious Adverse Device Effect (USADE): Serious adverse effect which by its nature, incidence, severity or outcome has not been identified in the current risk assessment.

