15.3.1 Investigator reporting Responsibilities

Investigators must report to the sponsor, without delay (immediately) and not later than 3 calendar days after his awareness, all adverse device effects (ADEs), device deficiencies and serious adverse events (SAEs) study subjects experience during participation in this investigation.

Each reported event must be appropriately documented to include the event's serious criterion, relatedness, treatment, and resolution. All reported events that remain unresolved should be re-assessed until the event resolves or the subject's study participation is complete. In the event of subject death, the investigator will make reasonable effort to obtain a death summary, autopsy report, etc.

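### The adverse event form triggers for stimulation pain in 7.5.1.3.1 are narrower than the adverse device effect rules in 15.1 and 15.3.1, so pain relieved by a setting change could go uncounted

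*Combined protocol and SAP*

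**What the plan says.** Section 7.5.1.3.1 of the combined protocol and SAP gives two instructions for putting stimulation pain on the adverse event form (page 11):

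- Trigger 1: "If stimulation settings cannot be adjusted or the stimulation cannot be applied without eliciting patient discomfort or pain due to the stimulation", an adverse event is marked on the daily form and the adverse event form is completed.
- Trigger 2: "In the event of pain that cannot be eliminated by reducing stimulation intensity then it should be recorded as such" on the adverse event form.

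Between the two stands an unconditional instruction: "Stimulation pain should be assessed daily using verbal and/or non-verbal cues from the patient using the visual analog scale shown below". Cross-over controls follow the same section (7.5.1.3.2).

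The general rules are wider. Section 15.1 has "Adverse Device Effect (ADE): Adverse event related to the use of an investigational medical device", and it defines an adverse event without regard to duration or reversibility. Section 15.3.1 obliges investigators to report, within 3 calendar days of awareness, "all adverse device effects (ADEs), device deficiencies and serious adverse events (SAEs) study subjects experience during participation in this investigation". Section 5.2 lists stimulation pain among the anticipated device effects with no condition attached: "Pain due to stimulation; 0 occurrences out of 10 patients".

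Device-related adverse events are an ancillary safety outcome (7.2.3), and section 8 gives no further case definition for them. The primary safety endpoint is limited to serious ADEs (8.4.1).

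**The concern.** Section 7.5.1.3.1 is the only place that tells site staff when stimulation pain belongs on the adverse event form, and both conditions describe pain that adjustment did not resolve. A coordinator working from that section could reasonably file nothing for pain that went away after a setting was changed. A colleague working from 15.1 and 15.3.1 would report the same episode. Both could claim to have followed the protocol.

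Three uses of the data depend on what is filed: the device-related adverse event outcome, counted as subjects with the event (8.2); the comparison of adverse event incidence between arms, which can pause implants (7.5.1.7); and the Medical Monitor's review of site-reported ADEs (section 16). Stimulation pain can arise only in stimulated patients, so any omission lowers the count in the treatment arm and in cross-over controls, and not in unstimulated controls. Identifying safety concerns is a stated secondary objective (6.2), and the data are meant to inform a pivotal trial (8.1).

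**Working it through.** **Comparison of the rules.** No figure in the plan needs reproducing. The check is to take each course that stimulation pain could follow and ask what each rule requires.

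| Course of the pain | Trigger 1 (7.5.1.3.1) | Trigger 2 (7.5.1.3.1) | 15.1 with 15.3.1 |
|---|---|---|---|
| Relieved by lower intensity | not met | not met | reportable if an untoward occurrence |
| Not eliminated by lower intensity, relieved by another change such as burst mode | arguably not met | met | reportable if an untoward occurrence |
| Not relieved by any adjustment | met | met | reportable |

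Row 1 is the conflict with section 15. Row 2 shows that the two triggers differ: the first concerns adjustment in general, the second names intensity alone. The first also covers discomfort, while the second mentions only pain.

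**Is the pain recorded elsewhere?** The daily visual analog assessment applies whether or not the pain persists. However, 7.5.1.3.1 assigns rhythm observations and stimulator settings to page 5 and names no form for the pain score. Tables 2a to 2d list no pain assessment, and neither 7.2.3 nor 8.4 has a pain-score outcome. Nothing links the score to the device-related adverse event count.

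**What the pilot rules out.** Input: 0 of 10 stimulated patients (5.2). The one-sided 95% upper bound is 1 − 0.05^(1/10) = 25.9%; the exact two-sided 95% upper limit is 1 − 0.025^(1/10) = 30.8%. Section 5.2 does not say which recording rule produced the zero.

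**Scale, by assumption only.** With 30 subjects and half stimulated from ICU entry (synopsis), the treatment arm has about 15. Section 4.2 expects 2 to 3 controls still ventilated at 5 days, so about 17 to 18 patients may be stimulated. The documents give neither a pain rate nor the share relieved by adjustment. For the 15 treatment patients, let p be the assumed rate of any stimulation pain and s the assumed share relieved and not filed. Expected patients with pain = 15p; expected patients on forms = 15p(1 − s).

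| p | Any pain | On forms, s = 50% | On forms, s = 80% |
|---|---|---|---|
| 10% | 1.5 | 0.75 | 0.3 |
| 20% | 3.0 | 1.5 | 0.6 |
| 40% | 6.0 | 3.0 | 1.2 |

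At p = 20%, the chance of at least one patient with pain is 1 − 0.80^15 = 96.5%. The chance of at least one on a form is 1 − 0.90^15 = 79.4% with s = 50%, and 1 − 0.96^15 = 45.8% with s = 80%. These figures assume that every relieved case goes unfiled, which is the extreme.

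**The case against.** The strongest reply is that 7.5.1.3.1 says when a form must be completed, and does not say that it must be completed in no other case. The all-ADE rule in 15.3.1 still binds, 7.5.1.7 and Tables 2b to 2d call for ADE monitoring, and trigger 2 can be read as asking for a descriptor on the form. This stands. A reader might infer that the protocol excludes relieved pain, or records pain only when reprogramming in general fails. The text supports neither: there is no exclusion, and trigger 2 refers to intensity alone. What remains is an unreconciled conflict that permits omission.

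A reader might also infer that an efficacy signal is hidden, since 3.6.4.2 says of burst mode "The trade-off of burst modulation settings is a reduction in diaphragm recruitment". The documents do not support this. Stimulator settings go on page 5, which is completed for each patient each day (7.5.1.3), so a pain-driven change of setting can be seen with or without an adverse event form.

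A third point is that programming is meant to be limited by comfort, so brief discomfort during a programming step may not be an untoward medical occurrence. That is a fair point, and it argues against making every momentary sensation an ADE.

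Finally, the outcome is ancillary and descriptive in a 30-patient lead-in study, and pain relieved by an adjustment would rarely be serious. This limits the importance of the point without removing the conflict.

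**Conclusion.** The point holds as a conflict between recording rules. The triggers in 7.5.1.3.1 are narrower than 15.1 and 15.3.1 and are inconsistent with each other. A literal reading of 7.5.1.3.1 could understate the outcome in 7.2.3 and the comparison in 7.5.1.7. The primary serious-ADE endpoint is essentially unaffected.

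The size cannot be established. The pilot is compatible with a pain rate up to about 26%, and every undercount shown above rests on assumed rates and on sites not applying 15.3.1. It would be wrong to conclude that the trial will report zero pain while a given number of patients had it. Severity is minor to moderate; this is a cheap improvement.

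**What to change.** Reconcile 7.5.1.3.1 with 15.1 and 15.3.1 in three steps:

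1. State that stimulation pain meeting the 15.1 definition is recorded as an ADE whether or not a setting change relieves it. One rule then replaces the two differing triggers, and the 15.1 definition leaves room for judgement about momentary discomfort during programming.
2. State that the daily visual analog score is entered on the daily post-op form (page 5).
3. Report the number of stimulated patients with stimulation pain, split into resolved by adjustment and not resolved, so that brief discomfort does not obscure persistent pain.

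The cost is a short edit, possibly one added form field, some extra mild-event forms with their 3-day reports, and a higher reported ADE count. Only recording and reporting change; programming and care do not.
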